5.4. SAFETY ANALYSIS SET [SAF]

All patients who have received any portion of ANB020 or placebo infusion. The safety analysis set will be used for all safety analyses. Patients will be considered according to their actual treatment received.

5.5. PHARMACOKINETIC ANALYSIS SET [PK]

All patients who have received ANB020 and have at least one post dose serum concentration data value available for ANB020 without any events or protocol deviation deemed to affect PK assessments. The PK analysis set will be used for all PK analyses.

5.6. PHARMACODYNAMIC ANALYSIS SET [PD]

All patients who have received at least one dose of ANB020 or placebo and provide at least one evaluable post dose PD measurement without any events or protocol deviation deemed to affect PD assessment. The PD analysis set will be used for all PD analyses.

6. GENERAL CONSIDERATIONS

The following descriptive statistics will be presented in summary tables:

Continuous variables: will be summarized by treatment group using number of valid cases (n), mean, median, standard deviation (SD), minimum, and maximum.

Categorical variables: will be summarized by treatment group using frequency tables [frequencies (n) and percentages (%)]. Percentages are routinely based on the total category count excluding the missing category if not otherwise mentioned. Missing category with zero count will not be presented.

In general, for non-PK/PD data, the number of decimal places displayed for each statistic will be determined as follows:

Document: \\ieedc-nas01a\biosdata\AnaptysBio\ANB020\CYA74393\Biostatistics\Documentation\SAP\Final2018-02-07
Author: [REDACTED] Version Number: Final 1.0
Version Date: 07Feb2018

Template No: CS_TP_BS016 Revision 4
Effective Date: 01Apr2016

Reference: CS_WI_BS005

STATISTICAL ANALYSIS PLAN

AnaptysBio Inc
PROTOCOL ANB020-003
Page 16 of 36

Mean and median: 1 more than the number of decimal places allotted in the raw data received from data management.

Standard deviation: 2 more than the number of decimal places allotted in the raw data.

Minimum and maximum: equal to the number of decimal places allotted in the raw data.

Percentages: All percentages between 0 and 100 will be rounded to one decimal unless there is a need to report more than one decimal for percentages.

Ranges will be reported to the same number of decimal places displayed by the laboratory.

P-values, if any, shall be reported to four decimal places or as <0.0001.

Pharmacokinetic parameters will be rounded for reporting purposes both in the summary tables and by-subject listings. For the calculation of descriptive statistics and the statistical analysis, rounded values as presented in the data listings will be used. All data will be reported and analyzed with the same precision as the source data regardless of how many significant figures or decimals the data carry. For most derived PK parameters, 3 significant digits will be used as the standard rounding procedure, with the following exceptions:

Parameters directly derived from source data [e.g., maximum observed concentration (C_{max})] will be reported and analyzed with the same precision as the source data.

Parameters derived from actual elapsed sample collection times [e.g., time to maximum observed concentration (t_{max})] will be reported in hours with 2 decimal places.

Apparent terminal rate constant (λ_z) will be reported with 4 decimal places.

For PK data, reporting of mean (arithmetic and geometric), SD, and median will carry 1 more significant figure than the source data. Minimum and maximum will carry the same number of significant figures as the source data. The bounds of any confidence intervals (CIs) will be reported with 2 decimals, and coefficient of variation (CV) will be reported as a percentage to 1 decimal place.

Extra measurements (such as unscheduled or repeat assessments) will not be included in the descriptive statistics, but will be included in subject listings. Pharmacokinetic summaries will be presented for all subjects in the PK analysis set as defined in [Section 5.5](#). Similarly, PD summaries will be presented for all subjects in the PD analysis set as defined in [Section 5.6](#). Data from subjects excluded from an analysis set will be included in the data listings, but not in the summaries.

Document: \\ieedc-nas01a\biosdata\AnaptysBio\ANB020\CYA74393\Biostatistics\Documentation\SAP\Final2018-02-07
Author: [REDACTED] Version Number: Final 1.0
Version Date: 07Feb2018

Template No: CS_TP_BS016 Revision 4
Effective Date: 01Apr2016

Reference: CS_WI_BS005

STATISTICAL ANALYSIS PLAN

AnaptysBio Inc
PROTOCOL ANB020-003
Page 17 of 36

6.1. REFERENCE START DATE AND STUDY DAY

The reference start date is defined as the day of the first dose of study medication (Day 1 is the day of the first dose of study medication), and will appear in every listing where an assessment date or event date appears.

The study day will be calculated from the reference start date, and will be used to show start/stop day of assessments and events.

If the date of the event is on or after the reference date then:

Study Day = (date of event – reference date) + 1

If the date of the event is prior to the reference date then:

Study Day = (date of event – reference date)

If the event date is partial or missing, Study Day, and any corresponding durations will appear partial or missing in the listings.

Refer to [Appendix 1](#) for more details.

6.2. BASELINE

The nearest non-missing measurements taken prior to ANB020 or placebo administration, i.e., reference start date, will be considered as baseline. If the last non-missing measurement and the reference start date coincide, that measurement will be considered baseline, but Adverse Events (AEs) and medications commencing on the reference start date will be considered post-baseline.

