### **Criteria for Monitoring and Stopping the Oral Food Challenge**

The Investigator or Sub-Investigator (clinician) should be in the study center during BPCFC.

Monitoring will include recording the vital signs before starting the initial placebo challenge, after completion of the placebo challenge, before starting the initial peanut challenge, upon completion of the final peanut challenge, and 2 hours after completion of the final peanut challenge. (See [Section 7.1.3](#) for more details). A physical examination will be conducted before starting the initial placebo food challenge and upon completion of the final peanut challenge (prior to discharge). For patients with a history of asthma, peak flow or spirometry will be collected before starting the initial placebo challenge and again before starting the initial peanut challenge. The time of dose administration will be recorded. The OFC Symptom Scoring System will be used before starting the initial placebo challenge, after completion of the placebo challenge, before starting the initial peanut challenge, upon completion of the final peanut challenge, and 2 hours after completion of the final peanut challenge.

At the first sign of an objective allergic reaction, the challenge will be stopped and the patient will be immediately assessed and treated accordingly. The EpiPen (1:1000) should be readily available with the patients at the start of the challenge and the Investigator should confirm the availability of other emergency medications and equipment (IV fluid, Benadryl, oxygen, Ambubags, etc.) at the study center. A standard anaphylaxis treatment plan is presented in [Section 16.0 \(Appendix IV\)](#). Any treatments given will be recorded along with the time given and clinical status of the patient. The patient will continue to be assessed and observed as the PI or Sub-Investigator deems appropriate.

A longer observation period may be warranted prior to proceeding with the next dose or discontinuation depending on the patient's clinical status and will be at the judgement of the Investigator.

All patients should have an emergency treatment plan available upon discharge from the study center regardless of the outcome of the study challenge and an EpiPen readily available.

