2.2. SECONDARY OBJECTIVES

To compare the symptoms to peanut antigen challenge on Day 14 using the Oral Food Challenge (OFC) Symptoms Scoring Assessment Tool after administration of ANB020 or placebo compared to baseline peanut BPCFC symptoms

To describe the limited pharmacokinetics (PK) of ANB020 following a single, intravenous (IV) dose

Document: \\ieedc-nas01a\biosdata\AnaptysBio\ANB020\CYA74393\Biostatistics\Documentation\SAP\Final2018-02-07
Author: [REDACTED] Version Number: Final 1.0
Version Date: 07Feb2018

Template No: CS_TP_BS016 Revision 4
Effective Date: 01Apr2016

Reference: CS_WI_BS005

STATISTICAL ANALYSIS PLAN

AnaptysBio Inc
PROTOCOL ANB020-003
Page 12 of 36

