17.2.3. ANALYSIS OF SECONDARY EFFICACY ENDPOINT

The analysis of the secondary efficacy endpoint will be carried out in the similar way as of primary efficacy endpoint for FAS population.

Document: \\ieedc-nas01a\biosdata\AnaptysBio\ANB020\CYA74393\Biostatistics\Documentation\SAP\Final2018-02-07
Author: [REDACTED] Version Number: Final 1.0
Version Date: 07Feb2018

Template No: CS_TP_BS016 Revision 4
Effective Date: 01Apr2016

Reference: CS_WI_BS005

STATISTICAL ANALYSIS PLAN

AnaptysBio Inc
PROTOCOL ANB020-003
Page 24 of 36

For analysis of secondary PK endpoints, refer to [Section 19](#) for details.

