- P-value is obtained using ANCOVA model with treatment as fixed effect and baseline value as covariate

Programming Note: Refer SAP for Model

Table 14 2 2 1
OFC Symptom Score – Full Analysis Set

Visit	Statistics	ANB020 (N=XX)	Placebo (N=XX)
Baseline (Prior to challenge 1)	n	xx	xx
	Mean (SD)	xx x (xx xx)	xx x (xx xx)
	Median	xx x	xx x
	Min, Max	xx, xx	xx, xx
Prior to challenge 2	----		
After completion of challenge 1	----		
After completion of challenge 2	----		
2 hours after the challenge completion	----		
Unscheduled time point	----		
 Day 14			
Prior to challenge 1	n	xx	xx
	Mean (SD)	xx x (xx xx)	xx x (xx xx)
	Median	xx x	xx x
	Min, Max	xx, xx	xx, xx
Change from Baseline to Prior to challenge 1 of Day 14	n	xx	xx
	Mean (SD)	xx x (xx xx)	xx x (xx xx)
	Median	xx x	xx x
	Min, Max	xx, xx	xx, xx
 Day 45			
Prior to challenge 1	n	xx	xx
	Mean (SD)	xx x (xx xx)	xx x (xx xx)
	Median	xx x	xx x

Document: \\ieedc-nas01a\biosdata\AnaptysBio\ANB020\CYA74393\Biostatistics\Documentation\SAP\Draft\2018-02-07
Author: [REDACTED]

Version Number: Draft 3.0
Version Date: 07Feb2018

Table 14 2 2 1
OFC Symptom Score – Full Analysis Set

Visit	Statistics	ANB020 (N=XX)	Placebo (N=XX)
	Min, Max	xx, xx	xx, xx
Change from Baseline to time point of Day 45	n	xx	xx
	Mean (SD)	xx x (xx xx)	xx x (xx xx)
	Median	xx x	xx x
	Min, Max	xx, xx	xx, xx

Source: Listing 16 2 2 1

Note:

- N is the number of patients within each treatment group under Full Analysis Set
- Baseline is defined as the nearest non-missing value before first dose of study medication

Programming Note: Continue this table for all available visits and respective change from baseline

Table 14.2.2.2
Secondary Efficacy: Change from Baseline in OFC Symptom Score at Day 14 – Full Analysis Set

	Treatment LSMEANS (SE)	Treatment Difference ANB020 vs Placebo (Standard Error)	95% CI for Difference	p-value
ANB020	Placebo	xxxx xxx (xxxx xxx)	xxx xx (xxx xxx)	(xxx xx, xxx xx)

Note:

- P-value is obtained using ANCOVA model with treatment as fixed effect and baseline value as covariate

Programming Note: Refer SAP for Model

Table 14 2 3 1
Change from Baseline in Total Cumulative Tolerated Peanut Dose (Unit) During BPCFC and OFC Symptom Score at Day 45 – Full Analysis Set

Endpoint	Treatment LSMEANS (SE)		Treatment Difference ANB020 vs 95% CI for Difference (Standard Error)	p-value
	ANB020	Placebo		
Total Cumulative Tolerated Peanut Dose During BPCFC	xxxx xxx (xxxx xxx)	xxxx xxx (xxxx xxx)	xxx xx (xxx xxx)	(xxx xx, xxx xx)

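### For the OFC symptom score, neither baseline stated in the SAP is the screening peanut reaction, so the per-arm changes from baseline need not measure change in reaction severity

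*SAP*

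**What the plan says.** The secondary objective (Protocol 3.2, SAP 2.2) is about symptoms on Day 14 "after administration of ANB020 or placebo compared to baseline peanut BPCFC symptoms". The comparator is therefore the patient's own reaction in the screening peanut challenge.

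SAP 6.2 defines baseline for all measurements: "The nearest non-missing measurements taken prior to ANB020 or placebo administration, i.e., reference start date, will be considered as baseline". It makes no exception for the OFC score.

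The shell of Table 14.2.2.1 gives a different definition. Its first row begins "Baseline (Prior to challenge 1", and the only Day 14 change row it writes out is "Change from Baseline to Prior to challenge 1 of Day 14". Its footnote then repeats the nearest-value rule of 6.2. The Baseline block also lists the other scoring times, among them the one after completion of challenge 2.

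Protocol 6.1.1 and 7.1.3 schedule five scores per challenge visit: before and after the placebo challenge, before the peanut challenge, and then "upon completion of the final peanut challenge, and 2 hours after completion of the final peanut challenge". On reactions, Protocol 6.1.1 says: "At the first sign of an objective allergic reaction, the challenge will be stopped and the patient will be immediately assessed and treated accordingly".

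SAP 17.2.1 names the endpoint as the OFC clinical scores on Day 14, without a time point. SAP 17.2.3 adds only this: "The analysis of the secondary efficacy endpoint will be carried out in the similar way as of primary efficacy endpoint for FAS population". Table 14.2.2.2 has room for one result, with an LS mean change for each arm, the difference, its 95% CI and a p-value.

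**The concern.** A change from baseline in reaction severity needs a reaction at both ends. The SAP states two baselines that disagree. One comes before any peanut has been eaten. The other comes two hours after the challenge, when a treated patient's symptoms may have gone. If a Day 14 reaction score is set against either of them, a patient whose reaction became milder can show a rise in score.

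The tested score is also open. With two baselines, five Day 14 time points and two obvious ways of combining items (sum or maximum), the text admits 2 x 5 x 2 = 20 specifications. With only the two post-peanut time points it admits 2 x 2 x 2 = 8. A programmer would have to choose one for the only secondary efficacy endpoint.

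**Working it through.** The plan has no figure to reproduce here: Protocol 9.1 gives no power calculation, SD or effect size. The check is to trace which score each rule selects and then see what that does to the table.

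**Inputs from the documents.** Placebo is given first and peanut second (Protocol 5.7.3), so challenge 2 is the peanut challenge. Before dosing, the OFC tool is used only at screening (Protocol Table 4.1). Planned arms are 15 and 5 (Protocol 6.2.2). Appendix II has 4 skin + 5 nasal + 1 chest + 4 abdominal = 14 items graded 0 to 3, so a sum runs from 0 to 42 and a maximum from 0 to 3.

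**Step 1. Which screening score is baseline?**

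| Screening score | Content | Selected by |
|---|---|---|
| Before challenge 1 | No challenge food yet | Row label of shell 14.2.2.1 |
| After challenge 1 | After placebo | None |
| Before challenge 2 | Before peanut | None |
| On completion of challenge 2 | Peanut reaction | The objective |
| 2 hours later | After any treatment | SAP 6.2 and the shell footnote |

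If the 2-hour score is missing, 6.2 falls back to the completion score, but only by accident.

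**Step 2. One patient (assumed values).** Screening scores are 0 before the challenge, 12 at reaction and 1 at two hours. The Day 14 completion score is 6, so the reaction has halved.
- Against the screening reaction: 6 - 12 = -6.
- Against the pre-challenge score: 6 - 0 = +6.
- Against the 2-hour score: 6 - 1 = +5.
- The one Day 14 row the shell writes out, pre-challenge to pre-challenge: 0 - 0 = 0 if the patient is also symptom-free before the Day 14 challenge.

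**Step 3. Arm means (assumed values).** All patients react at screening with mean score 6. On Day 14, 50% of ANB020 and 10% of placebo patients do not react, and reactors again average 6. Day 14 means are 6 x 0.5 = 3.0 and 6 x 0.9 = 5.4. Let r be the share of reactors treated before the 2-hour score and f the share of the score that treatment removes. The 2-hour baseline mean is then 6 x (1 - r x f).

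| Baseline | Mean | Change, ANB020 | Change, placebo | Difference |
|---|---|---|---|---|
| Screening reaction | 6 | -3.0 | -0.6 | -2.4 |
| Pre-challenge | 0 | +3.0 | +5.4 | -2.4 |
| 2-hour, r 0.5, f 0.3 | 5.1 | -2.1 | +0.3 | -2.4 |
| 2-hour, r 1, f 0.9 | 0.6 | +2.4 | +4.8 | -2.4 |

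With the 2-hour baseline, the ANB020 change turns positive once 6 x (1 - r x f) falls below 3.0, that is, r x f above 0.5. The placebo change turns positive once r x f exceeds 0.1. The difference between arms never moves.

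**Step 4. Precision.** For correlation rho between baseline and Day 14, approximately SE = SD x sqrt(1 - rho^2) x sqrt(1/15 + 1/5), with 17 df (t = 2.11).

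| rho | SE / SD | 95% CI half-width / SD | SE with uninformative baseline, relative to this |
|---|---|---|---|
| 0 | 0.516 | 1.09 | 1 |
| 0.3 | 0.493 | 1.04 | 0.516 / 0.493 = 1.05 |
| 0.5 | 0.447 | 0.94 | 0.516 / 0.447 = 1.15 |
| 0.7 | 0.369 | 0.78 | 0.516 / 0.369 = 1.40 |

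A simulation with normally distributed severity and true correlation 9/13 = 0.69 agrees: the difference was about -3.9 under all three baselines, and the SE was 1.36 (reaction), 1.81 (2-hour) and 1.88 (pre-challenge), where 1.88 / 1.36 = 1.38.

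The Step 3 setting was also simulated, with SD 3, and non-reactors scoring 0 on Day 14. There the baseline predicts less. The pre-challenge SE relative to the reaction-baseline SE was about 1.0, 1.03, 1.09 and 1.22 at correlations 0.3, 0.5, 0.7 and 0.9. At 0.5 the SEs were 1.73 (reaction) and 1.78 (pre-challenge), power was about 23% and 24%, and rejection with no drug effect was 4.6% to 5.1%.

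**The case against.** **The shell can be read as time-matched.** Its Baseline block includes the score after completion of challenge 2, and Listing 16.2.6.2 separates visit from time point. Protocol 4.2 says the screening challenge supplies the baseline. On this reading each Day 14 score is paired with its own screening value, and the right pair exists. This largely stands as a plausible intention, so it would be wrong to say the SAP contains no valid pairing. But the reading is nowhere stated, the footnote and SAP 6.2 contradict it, and it still does not say which pair Table 14.2.2.2 tests.

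**The inference is robust.** With baseline as a covariate, ANCOVA gives the same contrast for change as for the raw score. Randomisation keeps that contrast unbiased whichever pre-dose score is used. This stands in full. In the Step 3 setting no power was lost.

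**The sign reversals come from pairings that no document writes out.** This also stands. The only written Day 14 row would show a change near zero in both arms. The reversals show what the stated baselines allow when set against a Day 14 reaction score. They do not predict what will be reported.

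**The study is exploratory.** Protocol 2.3 disclaims hypothesis testing and the trial is unpowered. That limits the seriousness, but the SAP still plans per-arm changes, a CI and a p-value for this endpoint.

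**Conclusion.** The point holds in limited form. Neither stated baseline is the screening peanut reaction named in the objective, and the tested Day 14 score is not identified. As a result, the per-arm changes in Table 14.2.2.2 need not measure change in reaction severity and can have the wrong sign. Some precision may be lost: roughly none to 40% in the SE for correlations of 0.3 to 0.7, depending on how scores are distributed. All scores, response rates and correlations above are assumptions; the documents give none.

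A reader might infer three stronger things that the documents do not support:
- That the wrong baseline biases the treatment comparison or inflates false positives. It does neither.
- That rescue treatment is known to shrink the drug effect on the Day 14 score. A completion score is scheduled, nothing shows how often it follows treatment, and the size of any shrinkage cannot be derived.
- That the plan needs a particular total score. The item rule is missing detail, and the choice belongs to the sponsor.

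This should be corrected before database lock. It does not threaten the primary analysis.

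**What to change.** In SAP 17.2, and in 17.3 for Day 45, add: *The analysed OFC score is the one taken upon completion of the peanut challenge (After completion of challenge 2). Baseline is the same score from the screening peanut challenge, as an exception to 6.2.* State in the same place how the 14 item grades are combined.

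In the shell of Table 14.2.2.1, correct the baseline label, the change rows and the footnote so that each time point is paired with its own screening value.

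Report by arm and visit how many completion scores were taken after rescue. The data exist, since Protocol 6.1.1 requires: "Any treatments given will be recorded along with the time given and clinical status of the patient". Listing 16.2.6.2 carries the time of each score.

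The cost is a few sentences in a SAP amendment, one corrected shell and one small count table. The completion score is already scheduled and already has a shell row, so no visit or assessment is added. No protocol amendment, retrospective scoring or higher-of-two-scores rule is needed. The downside is that some completion scores may follow treatment and cannot be re-scored; the count shows how many.

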6.3. RETESTS, UNSCHEDULED VISITS AND EARLY TERMINATION DATA

Listings will include scheduled, unscheduled, retest, and early discontinuation data.

6.4. WINDOWING CONVENTIONS

Not applicable.

6.5. STATISTICAL TESTS

All tests of treatment effects will be conducted at a 2-sided alpha level of 0.05, or with 2-sided 95% CIs.

Document: \\ieedc-nas01a\biosdata\AnaptysBio\ANB020\CYA74393\Biostatistics\Documentation\SAP\Final2018-02-07
Author: [REDACTED] Version Number: Final 1.0
Version Date: 07Feb2018

STATISTICAL ANALYSIS PLAN

AnaptysBio Inc
PROTOCOL ANB020-003
Page 18 of 36

6.6. COMMON CALCULATIONS

For quantitative measurements, change from baseline will be calculated as:

Test Value at Visit X – Baseline Value

6.7. SOFTWARE VERSION

All analyses will be conducted using SAS System® Version 9.2 or higher.

The non-compartmental PK analysis will be conducted using SAS System® and/or Phoenix WinNonlin® 6.4 or higher, and PK graphics will be prepared using SigmaPlot® 12.5, or higher.

7. STATISTICAL CONSIDERATIONS

7.1. ADJUSTMENTS FOR COVARIATES AND FACTORS TO BE INCLUDED IN ANALYSES

The change from baseline on Day 14 of tolerated peanut dose will be compared between ANB020 and placebo using an analysis of covariance (ANCOVA) with treatment as fixed effect and baseline results as a covariate. Similarly, the mixed model for repeated measures for analysis of exploratory endpoints will include baseline and baseline by visit terms as covariates.

7.2. MULTICENTER STUDIES

Not applicable as this is a single center study.

7.3. MISSING DATA

No imputations will be performed on missing data.

7.4. MULTIPLE COMPARISONS/ MULTIPLICITY

Not applicable.

7.5. EXAMINATION OF SUBGROUPS

No subgroups analysis will be performed for this study.

Document: \\ieedc-nas01a\biosdata\AnaptysBio\ANB020\CYA74393\Biostatistics\Documentation\SAP\Final2018-02-07
Author: [REDACTED] Version Number: Final 1.0
Version Date: 07Feb2018

Template No: CS_TP_BS016 Revision 4
Effective Date: 01Apr2016

Reference: CS_WI_BS005

STATISTICAL ANALYSIS PLAN

AnaptysBio Inc
PROTOCOL ANB020-003
Page 19 of 36

